9.2.5 Day 1 (\pm 2 days) of Cycle 3 and Beyond

The following procedures will be performed at this visit:

- Collection of weight and vital signs (heart rate, blood pressure, temperature)
- ECOG performance status
- Symptom based physical examination
- Completion of Quality of Life assessment questionnaires
- Laboratory Tests: Fasting not required.
 - Serum Chemistry
 - Hematology
 - Serum/urine pregnancy test for females of child-bearing potential only

■ [REDACTED]

■ [REDACTED]

■ [REDACTED]

- Concomitant medications
- Assessment of AEs

In addition to the above procedures, the clinical site will conduct a drug accountability review on the returned empty bottles and unused medications and will also review the dosing diaries to assess compliance with the dosing schedule.

9.2.6 Tumor Response Assessment Visits

Tumor response assessment should occur approximately every 8 weeks (\pm 5 days) for the first 12 months of a subject's participation in AIM-HN; thereafter, tumor response assessment should occur approximately every 12 weeks (\pm 5 days) until disease progression. The tumor response assessment schedule (every 8 or 12 weeks) should be maintained regardless of dosing delays or additional imaging assessments performed.

The following procedures will be performed at this visit:

- Radiographic Imaging:
 - CT scan with a contrast agent is the preferred imaging method and the same technique should be used at baseline and post-treatment assessments. CT scan coverage should encompass scans of the neck (including the skull base), chest and abdomen (including

the liver and adrenals). Any other areas of disease involvement should be scanned based on the subject's signs and symptoms.

- Transfer of tumor scans and related clinical information to IRF

- [REDACTED]
- [REDACTED]
- [REDACTED]
- [REDACTED]
- [REDACTED]
- [REDACTED]
- [REDACTED]
- [REDACTED]
- [REDACTED]
- [REDACTED]
- [REDACTED]
- [REDACTED]
- [REDACTED]
- [REDACTED]
- [REDACTED]
- [REDACTED]
- [REDACTED]
- [REDACTED]
- [REDACTED]
- [REDACTED]
- [REDACTED]
- Concomitant medications
- Assessment of AEs
- [REDACTED]

9.2.7 End of Treatment Visit

The following assessments will occur approximately 30 days (± 7 days) after the last administration of study drug or immediately before the administration of another anti-cancer drug, whichever takes place first:

- Complete physical examination
- Weight
- Vital signs (heart rate, blood pressure, temperature)
- ECOG performance status.
- Completion of Quality of Life assessment questionnaires
- Laboratory tests: Fasting is not required.
 - Serum Chemistry
 - Hematology

- Serum/urine pregnancy test for females of child-bearing potential only
- Concomitant medications
- Assessment of AEs
- Radiographic Imaging: *Applies only for subjects who terminated treatment for reasons other than death or disease progression.* In these subjects, imaging should be performed at the End of Treatment visit if not done within the prior 8 weeks or if a tumor assessment is required for the confirmation of response.
 - CT scan with a contrast agent is the preferred imaging method and the same technique should be used at baseline and post-treatment assessments. CT scan coverage should encompass scans of the neck (including the skull base), chest and abdomen (including the liver and adrenals). Any other areas of disease involvement should be scanned based on the subject's signs and symptoms.
 - Transfer of tumor scans and related clinical information to IRF
- Conduct drug accountability and diary review on the returned empty bottles and unused medications.

9.2.8 Follow up Visit

Follow up visit(s) are required only for subjects who terminated treatment for reasons other than disease progression and should occur approximately every 8 or 12 weeks (± 5 days) until disease progression. If the subject initiates a new anticancer therapy without evidence of disease progression by RECIST v1.1 criteria, tumor assessments should continue until there is evidence of disease progression unless withdrawal of subject's consent to study procedures.

The assessments to be conducted at these visits are:

- Ascertainment of details of any new anti-cancer treatments/surgeries (name, dates (start, end), treatment outcome (response and response criteria), duration of response)
- Radiographic Imaging: to be performed if not done within the prior 8 weeks or if a tumor assessment is required for the confirmation of response.
 - CT scan with a contrast agent is the preferred imaging method and the same technique should be used at baseline and post-treatment assessments. CT scan coverage should encompass scans of the neck (including the skull base), chest and abdomen (including the liver and adrenals). Any other areas of disease involvement should be scanned based on the subject's signs and symptoms.
 - Transfer of tumor scans and related clinical information to IRF

- Assessments of AEs and concomitant medications may also be conducted if AEs were not resolved at the time of the End of Treatment visit.

9.2.9 Follow Up Contact

Upon disease progression or withdrawal of consent for additional study procedures, follow up contact with the subject and/or caregiver(s) (e.g. electronic technology-based, telephone or in person) is to occur approximately every 12 weeks (\pm 1 week) for survival and the use of subsequent therapy until End of Study (see [Section 6.7.1](#)). Information on survival and subsequent anticancer therapy for HNSCC will be collected including name, dates (start, end), treatment outcome (response and response criteria), duration of response, date of progression. Information will also be collected on subsequent cancer surgery(ies) for HNSCC including date of surgery. Information will be collected on subsequent radiological treatments for HNSCC including anatomical site(s) and date(s) of radiation treatment.

9.3 SEQ-HN

The evaluations to be performed for HRAS wildtype HNSCC subjects enrolled in SEQ-HN are summarized in [Table 3](#). The following subsections apply to HRAS wildtype HNSCC subjects participating in SEQ-HN.

9.3.1 Screening Procedures

A signed ICF must be obtained before any study-specific evaluations are performed and should be documented in the subject's medical chart. A separate consent will be obtained for HRAS mutation pre-screening and is further detailed in [Section 9.1](#).

The following evaluations and procedures will be performed during screening:

- Signed ICF for participation in the SEQ-HN portion of this study
- Collection of HRAS wildtype status (blood sample and tissue sample)
- Inclusion/exclusion criteria evaluation

9.3.2 Study Enrollment

The following information will be collected from enrolled subjects:

- Demographics
- Disease history including:
 - Primary diagnosis, date of initial diagnosis, stage of disease at diagnosis, anatomical disease site(s) at diagnosis
 - Current stage of disease

- Smoking and betel nut exposure
- Alcohol use
- HPV status
- Other relevant medical history
- First line systemic treatment for recurrent or metastatic HNSCC including:
 - Anatomical (organ) disease site(s) at the time of first line therapy for recurrent or metastatic disease
 - Performance status at the time of first line therapy for treatment of recurrent or metastatic disease.
 - Name of treatment
 - Dates of treatment (start, end).
 - Treatment outcome (response and response criteria), duration of response
 - Date of progression

In subjects who have not yet received or completed first line systemic treatment for recurrent or metastatic HNSCC, first line systemic treatment information (anatomical disease site, performance status, names and dates of treatment, treatment outcome, duration of response and date of progression) will be collected through follow-up contact (See [Section 9.3.4](#)).

- Other prior cancer therapy(ies) for HNSCC including:
 - Name(s) of treatment(s), dates (start, end)
 - Treatment outcome (response and response criteria), duration of response
 - Date of progressions
 - Prior cancer surgery(ies) for HNSCC including date of surgery.
 - Prior/current radiological treatments for HNSCC including anatomical site(s) and date(s) of radiation treatment.

9.3.3 On Study Visit

A blood sample will be collected from all control subjects during Weeks 16 – 24 since the time of SEQ-HN enrollment for the evaluation of acquired HRAS mutations during standard of care treatment, including surveillance or on treatment break. If a subject experiences disease progression prior to Weeks 16 - 24, the blood sample for HRAS mutational analysis should be collected at that time.

Subjects who are found to have an HRAS mutation following enrollment will be offered participation in AIM-HN (assuming all other eligibility criteria are met).

9.3.4 Follow Up Contact

Follow up contact with the subject and/or caregiver(s) (e.g. electronic technology-based, telephone or in person) is to occur approximately every 12 weeks (± 1 week) from the time of study enrollment through second line regimen initiation, consent withdraw or completion of AIM-HN. Additional follow up of the matched HRAS wildtype HNSCC patients enrolled into SEQ-HN may continue until all AIM-HN objectives are completed and KO-TIP-007 end of study is reached.

Information on survival and subsequent anticancer therapy for HNSCC may be collected by phone including name, dates (start, end), treatment outcome (response and response criteria), duration of response, date of progression. Information will also be collected on subsequent cancer surgery(ies) for HNSCC including date of surgery. Information will be collected on subsequent radiological treatments for HNSCC including anatomical site(s) and date(s) of radiation treatment.

10 ASSESSMENT OF EFFICACY

[Table 1](#), [Table 2](#), and [Table 3](#) summarize the study required evaluations.

10.1 Efficacy Parameters

The following subsections apply only to subjects participating in AIM-HN.

10.1.1 Efficacy Variables

Objective response (complete response and partial response) as determined by the subject's best tumor response, duration of response, and time to progression will be assessed using RECIST v1.1([Appendix I](#)) by IRF. Confirmation of response is required. An IRF charter providing the specific procedures will be filed with IRBs/IECs and regulatory authorities.

Local/Investigator tumor response assessments will be collected and used to inform patient care decisions.

10.1.2 Method and Timing

Radiological assessments of the tumor lesions will be made at screening (within 4 weeks prior to first study drug administration on Cycle 1 Day 1) and at least once approximately every 8 weeks (± 5 days) for 12 months, thereafter once approximately every 12 weeks (± 5 days). Additional tumor assessments may be conducted at the judgment of the Investigator.

Radiological assessments will be discontinued at the time of tumor progression. Subjects who discontinue treatment for reasons other than disease progression must continue tumor assessments until disease progression. Collection of response data may continue upon initiation of another anticancer therapy unless the subject withdraws their consent to study procedures.

Radiological assessments may also be conducted at treatment discontinuation (End of Treatment visit) if the reason for the treatment termination is other than disease progression and a tumor assessment was not done within 8 weeks before treatment discontinuation (assessment must be conducted before subsequent anti-tumor therapy is started). Scans at the End of Treatment visit will be also conducted if required to confirm response to treatment.

[figure not shown]
Lesions to be included in the tumor assessments should follow RECIST v1.1 (See [Appendix I](#)). CT scan with a contrast agent is the preferred imaging method and the same technique should be used at screening and post-treatment assessments. CT scan coverage at screening should encompass scans of the neck (including the skull base), chest and abdomen (including the liver and adrenals). Any other areas of disease involvement should be scanned based on the subject's signs and symptoms.

Subjects with contrast allergy or renal insufficiency may use non-contrast CT or MRI, whichever is required to adequately assess all disease. For subjects who develop a contraindication to contrast after screening scans are performed with a contrast agent, the decision to use non-contrast CT or MRI (enhanced or non-enhanced) should be based on tumor type, anatomic location of disease and should be optimized to allow for comparison to the prior scans if possible. The one exception where MRI would not be recommended is for the evaluation of parenchymal lung metastases. In this instance, CT would be preferred. If imaging of the brain is indicated, MRI of the brain with and without gadolinium should be performed for optimal evaluation of the brain. If MRI is medically contraindicated, CT of the brain with and without contrast would be suggested. Guidelines for imaging and instructions for transmission of the images to IRF will be provided to each study site.

10.2 Additional Variables

10.2.1 Population Pharmacokinetics

The blood samples for population PK analysis will be collected from subjects participating in AIM-HN at the time points described in [Table 9](#).

The time and date of blood sample collection will be collected and recorded in the eCRF. Additionally, on study visit days when a blood sample for population PK analysis is collected, the time, date and dosage (mg) of the subject's last dose of tipifarnib (most recent dose to the PK blood sample) will be collected and recorded in the eCRF.

The total blood volume to be collected for the purpose of characterizing the population PK of tipifarnib will be approximately [REDACTED]. Additional blood samples for the determination of tipifarnib plasma concentration may be collected at the discretion of the Investigator.

Samples for the evaluation of tipifarnib concentration will be collected, processed and shipped as detailed in the Laboratory manual.

10.2.2 Biomarkers

Additional variables to be examined as a part of this study include somatic mutations in submitted tumor tissue and plasma samples [REDACTED] (Witzig 2017). These variables may be examined in subjects enrolled in AIM-HN and in subjects enrolled in SEQ-HN.

Genetic testing will be/was performed using Sponsor approved local tests or through central testing designated by the Sponsor. Samples may be submitted to a laboratory CRO if deemed necessary by the Investigator or Sponsor or for convenience. Genetic markers (mutation, gene expression) include, but are not limited to, a panel of oncogenes commonly mutated in HNSCC or other alterations that could be relevant for the biology or treatment of HNSCC. Gene expression analyses may include the characterization of alternative gene spliced transcripts, post-transcriptional modifications, gene fusions, changes in gene expression and unsupervised gene expression analyses.

11 ASSESSMENT OF SAFETY

The following subsections apply only to subjects participating in AIM-HN.

11.1 Safety Parameters

Adverse events will be graded according to the NCI CTCAE v5.0. Adverse events will be summarized by relationship to study drug and severity. The safety profile of the IP will be assessed through the recording, reporting and analyzing of baseline medical conditions, AEs, physical examination findings including vital signs and laboratory tests. Comprehensive assessment of any apparent toxicity experienced by the subject will be performed throughout the course of the study, from the time of the subject's signature of informed consent for AIM-HN. Incidental findings on radiological scans will not be reported by the IRF. Study site personnel will report any AE, whether observed by the Investigator or reported by the subject.

The IDMB will review all relevant safety data on a regular basis.

11.2 Method and Timing

At each study visit, the subject will be queried on changes in his/her condition. During the reporting period of the study any unfavorable changes in the subject's condition will be recorded as AEs, whether reported by the subject or observed by the Investigator.

Complete, accurate and consistent data on all AEs experienced for the duration of the reporting period (defined below) will be reported on an ongoing basis in the appropriate section of the eCRF. Among these AEs, all SAEs must be additionally documented and reported using the Serious Adverse Event Report Form. It is important that each AE report include a description of the event, its duration (onset and resolution dates, including time when it is important to assess the time of AE onset relative to the recorded treatment administration time), its severity, its relationship with the study treatment, any other potential causal factors, any treatment given or other action taken (including dose modification or discontinuation of the IPs) and its outcome. In addition, serious cases should be identified, and the appropriate seriousness criteria documented. Specific guidance can be found in the eCRF completion and monitoring conventions provided by the Sponsor.

11.2.1 Monitoring of Subjects with Adverse Events

Any AE that occurs during the course of a clinical study and is considered to be possibly related to the IP must be monitored and followed up by the Investigator until stabilization or until the outcome is known unless the subject is documented as "lost to follow-up". Reasonable attempts to obtain this information must be made and documented. It is also the responsibility of the Investigator to ensure that any necessary additional therapeutic measures and follow-up procedures are performed. The Sponsor will actively follow-up and collect information on any AE that occurs during the course of a clinical study, however while this activity will continue for

any serious AEs until stabilization or until the outcome is known, it will be discontinued at the time of database lock for non-serious AEs.

11.2.2 Pregnancy and In Utero Drug Exposure

Only pregnancies considered by the Investigator as related to study treatment (e.g. resulting from a drug interaction with a contraceptive medication) are considered as AEs. However, all pregnancies with an estimated conception date during the study safety period must be recorded by convention in the AE page/section of the eCRF. The same rule applies to pregnancies in female subjects and in female partners of male subjects. The Investigator must notify the Sponsor in an expedited manner of any pregnancy using the Pregnancy Report Form, which must be transmitted according to the same process as described for SAE reporting.

Investigators must actively follow up, document and report on the outcome of all these pregnancies, even if the subjects are withdrawn from the study. The Investigator must notify the Sponsor of these outcomes using the Pregnancy Report Form, and in case of abnormal outcome, the Adverse Event Report Form when the subject sustains an event and the Parent-Child/Fetus Report Form when the child/fetus sustains an event.

Any abnormal outcome must be reported in an expedited manner, while normal outcomes must be reported within 45 days from delivery.

In the event of a pregnancy in a subject occurring during the course of the study, the subject must be discontinued from study medication immediately. The Sponsor must be notified without delay and the subject must be followed as mentioned above.

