 - b) If of child-bearing potential, subject must use a highly effective method of contraception, such as combined (estrogen and progestogen containing) hormonal contraception associated with inhibition of ovulation, progestogen-only hormonal contraception associated with inhibition of ovulation, intrauterine device, intrauterine hormone-releasing system, bilateral tubal occlusion, vasectomised partner or sexual abstinence. Both females and male subjects with female partners of child-bearing potential must agree to use a highly effective method of contraception from the first dose of tipifarnib, during tipifarnib treatment, and at least 28 days after last dose of tipifarnib for females and 90 days for males. Female subjects must have a negative serum or urine pregnancy test within 72 hours prior to start of trial medication.
 - c) Not breast feeding at any time during the study.
13. Written and voluntary informed consent understood, signed and dated.

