11.3 Adverse Event Reporting

11.3.1 Procedure for Reporting Adverse Events

The AE reporting period for safety surveillance begins when the subject is included into the study (date of first signature of AIM-HN informed consent) and continues through the study's post-treatment follow-up period, defined as approximately 30 days from the final administration of the study treatment or immediately before initiation of any other anticancer therapy, whichever comes first.

The Investigator is required to grade the severity/intensity of each AE. Investigators will reference the NCI-CTCAE v 5.0. This is a descriptive terminology that can be used for AE reporting. A general grading (severity/intensity) scale is provided at the beginning of the referenced document, and specific event grades are also provided. If a particular AE's severity/intensity is not specifically graded by the guidance document, the Investigator is to revert to the general definitions of Grade 1 through Grade 5 and use his or her best medical judgment.

The 5 general grades are:

- Grade 1: Mild

- Grade 2: Moderate
- Grade 3: Severe or disabling
- Grade 4: Life-threatening
- Grade 5: Death related to AE. Note: Death (Grade 5 as defined by NCI-CTCAE version 5.0) is mainly regarded as an outcome, to be documented as described below.

According to the Sponsor's convention, if a severity/intensity of Grade 4 or 5 is applied to an AE, then the Investigator must also report the event as an SAE as per [Section 11.4.2](#). However, a laboratory abnormality with a severity/intensity of Grade 4, such as low white blood cell count or increased ALT, is considered serious only if the condition meets one of the serious criteria described below.

In the case of death, the primary cause of death (the event leading to death) should be recorded and reported as an SAE. "Fatal" will be recorded as the outcome of this respective event; death will not be recorded as separate event. Only if no cause of death can be reported (e.g., sudden death, unexplained death), the death per se might be reported as an SAE.

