11.5 Adverse Event Follow-up

All subjects will be followed-up for safety through approximately 30 days after treatment discontinuation or until immediately before the administration of another anticancer treatment, whichever occurs first. Additional safety follow-up may be conducted if unresolved toxicity is present at the End of Treatment visit. The IDMB will provide periodic evaluations of safety and other data to ensure subject safety as well as the validity and scientific merit of the study.

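### The pregnancy recording window in Section 11.2.2 appears to close about 30 days after the last dose, although the protocol elsewhere sets 90 days for men; the notification duty beyond that point is ambiguous

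*Protocol*

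**What the plan says.** **Recording.** Protocol Section 11.2.2 states that "all pregnancies with an estimated conception date during the study safety period must be recorded by convention in the AE page/section of the eCRF". It then adds: "The same rule applies to pregnancies in female subjects and in female partners of male subjects". One window, set by conception date, therefore governs both groups.

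**The window.** The term *study safety period* has no definition of its own. The nearest match is the adverse event reporting period in Section 11.3.1. It opens at AIM-HN consent and "continues through the study's post-treatment follow-up period, defined as approximately 30 days from the final administration of the study treatment". The same sentence closes it sooner when a subject moves to a different cancer treatment. Section 11.5 agrees: "All subjects will be followed-up for safety through approximately 30 days after treatment discontinuation". So does the End of Treatment visit in Section 9.2.7: "The following assessments will occur approximately 30 days (± 7 days) after the last administration of study drug". The SAP also uses 30 days, both for its on-treatment safety period (Section 7) and for treatment-emergent events (Section 9.8.1).

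**Contraception periods.** Inclusion criterion 12b (Section 7.1.1) requires contraception for at least "28 days after last dose of tipifarnib for females and 90 days for males". Section 8.1.6.1 contains two figures. Its general paragraph gives a minimum of 4 weeks after the last dose for women and for men with partners of child-bearing potential. Its list for male subjects gives 90 days. That section also reports impaired fertility in rats of both sexes and names semen as a route by which a pregnant woman could be exposed.

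**Notification and outcome.** A later sentence in Section 11.2.2 requires expedited sponsor notification of *any pregnancy* on a separate form, with no conception window stated. The next paragraph asks for outcome follow-up of *all these pregnancies*.

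**After End of Treatment.** Follow Up Visits (9.2.8) cover new treatments, imaging, and adverse events only where unresolved. Follow Up Contacts (9.2.9) cover survival and subsequent therapy. Neither lists a question about pregnancy.

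**The concern.** The protocol names in utero and partner exposure as a hazard and, in two places, gives men 90 days after the last dose. Its recording rule borrows a window built for adverse events, which stops about a third of the way through those 90 days. That window also stops when another anticancer therapy begins. This is a sensible cut-off for attributing adverse events, but starting a new drug does not undo earlier exposure to tipifarnib.

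At stake is the capture of a few individually important cases. A partner pregnancy conceived in the later part of the 90 days need not go into the eCRF. Whether it must be notified and followed to outcome depends on how a site reads Section 11.2.2, and no scheduled contact would bring it to light. The point concerns the reporting window only, not how long contraception should last or which method to use.

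**Working it through.** The documents state no figure for this gap, so there is nothing to reproduce. The check is a day count.

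**Inputs**
- Male period after last dose: 90 days (criterion 12b; male list in 8.1.6.1).
- Female period after last dose: 28 days (criterion 12b).
- Competing figure for both sexes: at least 4 weeks, that is 28 days (8.1.6.1, general paragraph).
- End of safety period after last dose, *e*: about 30 days (11.3.1, 11.5). The End of Treatment visit allows 30 − 7 = 23 to 30 + 7 = 37 days (9.2.7). The period ends earlier, down to day 0, if another anticancer therapy starts (11.3.1).

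**Formulas**
- Men: uncovered days = 90 − *e*; share = (90 − *e*)/90.
- Women: uncovered days = max(0, 28 − *e*).

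| End of safety period, *e* | Men: uncovered of 90 | Women: uncovered of 28 |
|---|---|---|
| 37 (late visit) | 53 (58.9%) | 0 |
| 30 (nominal) | 60 (66.7%) | 0 |
| 23 (early visit) | 67 (74.4%) | 5 |
| 0 (new therapy at once) | 90 (100%) | 28 |

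The documents do not say how soon new therapy usually starts. For a start between day 0 and day 30, the uncovered part runs from 90 down to 60 days for men. For women it runs from 28 days down to none, reaching none at day 28.

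**Sensitivity to the male benchmark.** If the 4-week figure applied to men instead, 28 − 30 is negative, so there would be no gap at the nominal end. The 60 days depend on the 90-day figure.

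**Sensitivity to the denominator.** The male contraception period also covers treatment, and the safety period covers treatment in full. With T days from first to last dose, the uncovered share of the whole span is 60/(T + 90). At T = 30 this is 60/120 = 50%. At T = 77 it is 60/167 = 35.9%. Most of the period is uncovered only if the count starts at the last dose, or if T is below 30 days.

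**Would later contacts pick these cases up?** Follow Up Contacts are 12 weeks ± 1 week apart, that is 77 to 91 days. A contact near day 84 after the last dose would come before day 90 and too early to learn of a conception in the preceding weeks. One added question at one contact would therefore not cover the window.

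**The case against.** The strongest counter-argument is the notification sentence in Section 11.2.2. On its plain words it covers any pregnancy, through a separate form and the serious adverse event route. The safety-period limit is attached only to the eCRF page. A reader might infer from the recording rule that later partner pregnancies need not be reported and would never reach the sponsor. The documents do not support that inference. Equally, they do not settle the opposite reading. The sentence follows directly on the windowed rule, the outcome duty refers back to *all these pregnancies*, and a site can report only what it learns. Ambiguity is what stands.

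Four further objections have force:
- The safety period is not 30 days long. It runs from consent through all treatment, and 30 days is only its tail. A reader might infer that most of the male contraception period is unmonitored; over the whole span that is usually untrue, as the denominator check shows.
- The 90-day benchmark is itself contradicted within Section 8.1.6.1.
- Equating the undefined safety period with the one in Section 11.3.1 is an inference, and the eCRF completion conventions mentioned in Section 11.2 are not available. No other period in the documents fits, however.
- SAP Section 3 records early closure of the study, so an amendment would help only subjects still on treatment or within the window.

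These objections narrow the point. They do not remove the mismatch between the recording window and the 90 days.

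**Conclusion.** The point holds for recording. About 60 of the 90 post-dose days that the protocol gives for men (67%) lie outside the eCRF window. The range is 53 to 67 days over the End of Treatment visit window, and up to 90 days if new therapy starts immediately. For women there is ordinarily no gap; one arises only if the visit is early (up to 5 days) or new therapy starts within 28 days of the last dose.

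For sponsor notification and outcome follow-up, the conclusion is that the duty is unclear, not that it is absent, and that no contact after End of Treatment is designed to detect a pregnancy.

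This rests on two assumptions: that the safety period of Section 11.2.2 is the one in Section 11.3.1, and that the 90-day figure is the one that counts for men. The review does not judge which contraception period is right. The documents give no expected number of pregnancies; it is assumed to be small. No efficacy analysis is affected. This is a safety-capture weakness that should be corrected, not a threat to the trial's conclusions.

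**What to change.** 1. Reconcile Protocol Sections 7.1.1 (criterion 12b, repeated in the synopsis), 8.1.6.1, 11.2.2 and 11.3.1, including the 4-week and 90-day figures that stand side by side in 8.1.6.1.
2. In Section 11.2.2, replace the reference to the safety period with a dedicated pregnancy window. It should open no later than the first dose (the present period opens at consent, and keeping that start loses nothing). It should close at the end of whichever post-treatment contraception period the protocol retains for each sex, regardless of new anticancer therapy.
3. State that this one window governs eCRF recording, sponsor notification and outcome follow-up.
4. Add a pregnancy and partner-pregnancy question to the existing Follow Up Visits (9.2.8) and Follow Up Contacts (9.2.9). Continue it through the first contact late enough after the window closes to detect conceptions near its end.

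The cost is a short text change, one question at contacts that already take place, and a slightly longer reporting duty for sites. No new visit or sample is needed.
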